10.1.4 Sensitivity analyses

- The main analysis as described in Section 10.1.3 will be conducted based on the INV assessment.
- The analysis mentioned in Section 10.1.3 will be performed excluding the patients with no post-baseline assessment of response or with all post-baseline assessments categorized as “Unknown”. The analysis will be performed using the FAS based in both IRC and INV assessment.

10.2 Secondary objective 2

10.2.1 Objective

To determine the activity of a combination of LEN with MOR00208 in terms of progression-free survival (PFS).

10.2.2 Endpoint: Progression-free survival

PFS will be defined as the time (in months) from the date of the first administration of any study drug to the date of tumour progression or death from any cause (see Independent Review Charter version 4.3, 10-JUL-2018). The date of progression will be the first date for which progressive disease was assessed as the objective response. The tumour assessments will be derived according to the IWG treatment response criteria for malignant lymphoma (Cheson et al., 2007; see section 6.14), by an Independent Radiology/Clinical Review Committee (IRC). The review process will be defined in the IRC Charter.

10.2.3 Disease assessments

Disease assessments will be performed with either PET/CT scans or CT/MRI scans as per the schedule in Table 12.

STATISTICAL ANALYSIS PLAN

 MorphoSys AG
 MOR208C203

Table 12: Schedule of Tumour Assessments

Evaluation	Screening	C3 D1	C5 D1	C7 D1	C10 D1	C12 D28	C13 D1	Every 3 months	From C25 D1 onward once per year	EOT visit
Disease response assessment (PET/CT or PET/MRI)	X					X			X [§]	X
CT or MRI scan for tumour measurement and disease response assessment		X	X	X	X		X*	X	X	

*Can be done approx. 3 months after C12D28 PET/CT or PET/MRI assessment.

§Only if deemed necessary and not more frequently than once per year. A window of ± 2 weeks is allowed by the protocol for these assessments. Tumour assessments will continue until disease progression, death or study discontinuation (whichever occurs first).

10.2.4 Censoring rules

12.1.1 Censoring situations

If a patient is alive and progression-free at the date of the analysis (i.e., cut-off date), the patient will be censored, and the reason for censoring will be provided as per Table 13.

The date of last adequate tumor assessment is the date of the last tumor assessment with overall lesion response of CR, PR or SD before an event or a censoring reason occurred. In this case the last tumor evaluation date at that assessment is used. If no post-baseline assessments are available (before an event or a censoring reason occurred) the date of start date of treatment is used.

**Table 13: Censoring Rules**

Situation	Date of Progression or Censoring	Outcome	Censoring reason
Ongoing and No event until data cut-off	Date of last adequate tumour assessment	Censored	Ongoing
Discontinued the study with no event	Date of last adequate tumour assessment	Censored	Discontinued without event
No baseline tumour assessment	Date of C1D1	Censored	No baseline tumour assessment
Lost to follow-up	Date of last IRC tumour assessment (or C1D1 in case of study discontinuation w/o progression before any post-baseline assessment)	Censored	Lost to follow-up
Patient received non-study anti-DLBCL treatment before disease progression	Date of last adequate tumour assessment before start of non-study cancer treatment	Censored	New anti-cancer therapy started
Clinical Progression*	Date of last adequate tumour assessment	Censored for Analysis based on Investigator assessment only	Clinical Progression not validated by Cheson Criteria
PD by modality not including PET Scan is not confirmed by modality including PET Scan**.	Date of last adequate tumour assessment	Censored for Analysis based on Investigator assessment only	Non-PET PD not confirmed by PET.
Death before any date of PD assessment	Date of death	Progressed	
Death between adequate assessments	Date of death	Progressed	
Death or progression after two or more	Date of last adequate	Censored	Event documented

STATISTICAL ANALYSIS PLAN

 MorphoSys AG
 MOR208C203

Situation	Date of Progression or Censoring	Outcome	Censoring reason
missed visits	tumour assessment		after two or more missing tumor assessments
EOT after two or more missed assessments without disease progression	Date of Last adequate Tumour Assessment	Censored	Adequate assessment no longer available

Abbreviations: EOT = End of Treatment; IRC = Independent Review Committee; PD = progressive disease; CT = Computed tomography; PET = Positron emission tomography. *Progression as per Investigator's assessment and without meeting PD criteria according to Response Criteria for Malignant Lymphoma (Cheson et al., 2007). **The rule only applies in case a PET-including modality is performed after a non-PET including modality.

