6.6.2.3 Tumour Flare with LEN

Patients in this study should be monitored for tumour flare (TFR). TFR is defined as a sudden and tender increase in the size of the disease bearing sites, including the lymph nodes, spleen and/or the liver, often accompanied by low-grade fever, non-pruritic diffuse rash and in some cases, an increase in the peripheral blood lymphocyte counts. TFR is an expected toxicity with LEN, especially in patients with a high tumour burden and may mimic disease progression. Therefore, careful monitoring and evaluation is important prior to discontinuing a study patient for progressive disease in the initial cycles of LEN therapy. There are currently no laboratory or radiological tests to help distinguish TFR from progressive disease. The distinction should be made on clinical grounds, incorporating observations such as associated physical findings, laboratory findings, and pace of disease before and after the initiation of treatment. TFR should be recorded as an AE of interest (graded using the NCI-CTCAE 4.0 criteria) and not as progressive disease.

Treatment of TFR is at the discretion of the investigator and dependent on the severity, clinical situation and institutional standards.

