6.9 Start and end date for time to event variables

Assessment date

For each assessment (i.e. evaluation number), the **assessment date** is calculated as the latest of all measurement dates (e.g. X-ray, CT-scan) if the overall response at that assessment is CR/PR/SD/UNK/NE.

Otherwise - if overall response is progression – the assessment date is calculated as the earliest date of all measurement dates at that evaluation number.

Start dates

For all “time to event” variables, other than duration of response, the start date of study treatment will be used as the start date.

For the calculation of duration of response the following start date should be used:

Date of first documented response is the assessment date of the first overall response of CR or PR.

End dates

The end dates which are used to calculate ‘time to event’ variables are defined as follows:

- Date of death (during treatment as recorded on the treatment completion page or during follow-up as recorded on the study evaluation completion page or the survival follow-up page).
- Date of progression is the first assessment date at which the overall response was recorded as progressive disease.
- When there is no documentation of radiologic evidence of progression, and the patient discontinued for ‘Disease progression’ due to documented clinical deterioration of disease, the date of discontinuation is used as date of progression.
- If no post-baseline assessments are available (before an event or a censoring reason occurred) the start date of study treatment is used as the end date.

Calculation of ‘time to event’ variables

Time to event = End Date - Start date + 1 (in days).

When no post-baseline tumor assessments are available, the start date of study treatment will be used as end date (duration = 1 day).

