10.2.5 Main analysis

- The tumour assessments will be derived according to the IWG treatment response criteria for malignant lymphoma (Cheson et al., 2007), by an Independent Radiology/Clinical Review Committee (IRC). The review process will be defined in the IRC Charter.
- The distribution of PFS will be estimated using the Kaplan-Meier (K-M) method. The median PFS time along with 95% confidence intervals will be presented (Brookmeyer and Crowley 1982). 25th and 75th percentiles will be considered as well.
- The PFS probabilities at specific time points (1 month, 3 months, 6 months, 12 months, 18 months, 24 months, 30 months), and the associated 95% CIs (Greenwood formula) will be summarized.
- PFS events will be described according to the type of event (death, documented tumour progression).
- The reason for censoring will be tabulated.
- A plot of the Kaplan-Meier curve for PFS will be provided.
- The median follow-up time for PFS including a 95% confidence interval (Brookmeyer and Crowley 1982) will be calculated using the reverse Kaplan-Meier method.
- No formal hypothesis testing will be conducted.
- The main analysis will be conducted on the FAS for both the IRC and INV response assessment.

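### In the investigator-assessed PFS analysis (and the INV DoR sensitivity analysis), Table 13 censors a patient whose CT/MRI progression a following PET does not confirm; read literally, it ignores that PET and drops any later progression or death

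*SAP*

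**What the plan says.** The rule is one row of Table 13 in SAP 10.2.4. The situation is "PD by modality not including PET Scan is not confirmed by modality including PET Scan", the outcome is "Censored for Analysis based on Investigator assessment only", and the row has its own censoring reason. A footnote sets the trigger: "The rule only applies in case a PET-including modality is performed after a non-PET including modality". So a PET must have followed the CT or MRI and failed to confirm it.

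The row's date is the last adequate tumour assessment. Under Censoring situations, the SAP defines this as the "date of the last tumor assessment with overall lesion response of CR, PR or SD before an event or a censoring reason occurred".

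SAP 6.9 adds: "Date of progression is the first assessment date at which the overall response was recorded as progressive disease". It makes no provision for a later PD after an unconfirmed one.

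On status, SAP 10.2.5 says of PFS: "The main analysis will be conducted on the FAS for both the IRC and INV response assessment". SAP 10.2.6 also lists INV PFS as a sensitivity analysis. For DoR, 10.3.3 refers to Table 13, 10.3.4 makes the main analysis IRC only, and 10.3.5 has INV as a sensitivity analysis under the same censoring rules.

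**The concern.** A patient in this row has had a suspected progression checked with PET and not confirmed. The natural handling is to disregard the suspect reading, credit the PET and carry on. The row instead ends the INV record at a scan that normally precedes the suspect one.

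That conflicts with the endpoint. SAP 10.2.2 defines PFS as time to progression or death from any cause. Protocol 10.6.2.3 censors patients who have had neither, at their last available tumour assessment. Under this row, a patient who later progresses or dies can be censored, and at a date earlier than the last available assessment.

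At stake are the INV PFS curve, the INV DoR sensitivity analysis, and outputs that use INV PFS status: the concordance table (10.2.7), the batch-switch summaries (16.5.3) and the post-treatment survival subgroups (21.1).

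**Working it through.** The plan states no figure for this rule, so there is none to reproduce. The check is a reading of the text, followed by an illustration of size.

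**1. Which date the row gives.** The CT/MRI reading is PD, so it cannot be a CR/PR/SD assessment. The PET is what brings the censoring reason about, so it does not come before it. In the simple sequence of scan, CT PD, PET, the date is therefore the scan before the CT PD, or first dose if there was none.

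**2. Whether follow-up resumes.** No text in 6.9, 10.2.4 or 10.3.3 resumes it or ranks this row against a later PD or death.

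**3. Whether another planned analysis reverses the row.** In 10.2.6, the analysis that restores deaths covers missed visits only. SAP 20.9 changes three other rows (study discontinuation without event, new anti-DLBCL treatment, event after two or more missed visits) and keeps the rest. No planned INV PFS or DoR analysis undoes this row.

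**4. Effect on one patient.** With 28-day cycles, nominal day = (cycle - 1) x 28 + day. This gives C3D1 = 57, C5D1 = 113, C7D1 = 169, C10D1 = 253 and C12D28 = 336.

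- SD at day 169, CT PD at day 253, non-confirming PET at day 281, true PD or death at day 500. As written: censored at day 169. With continued follow-up: event at day 500.
- Event-free time not credited up to the PET = PET day - censoring day. A month is 30.4375 days (SAP 6.6). A PET 28 days after the CT is an assumption.

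| CT PD at | Censored at day | PET at day | Days lost (months) |
|---|---|---|---|
| C3D1 | 1 | 85 | 84 (2.8) |
| C5D1 | 57 | 141 | 84 (2.8) |
| C7D1 | 113 | 197 | 84 (2.8) |
| C10D1 | 169 | 281 | 112 (3.7) |
| C10D1 | 169 | 336 (C12D28) | 167 (5.5) |

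**5. Effect on the curve (illustration only).** Assumptions, none from the documents: exponential PFS with median 12 months, follow-up cut at 30 months, CT PD at C10D1, non-confirming PET 28 days later, censoring at C7D1. A random fraction of patients still event-free at the PET is affected, giving 2.9% or 5.9% of all patients. Their later hazard is 0.5, 1 or 2 times that of the others. Each cell shows continued follow-up, then the rule as written.

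| Share affected | Later hazard | 12-month PFS (%) | 24-month PFS (%) | Patients with a counted event (%) |
|---|---|---|---|---|
| 2.9% | 0.5 | 50.1, 49.4 | 25.7, 24.7 | 81.7, 80.3 |
| 2.9% | 1 | 50.1, 49.6 | 25.0, 24.8 | 82.3, 80.2 |
| 2.9% | 2 | 49.6, 49.5 | 24.3, 24.8 | 82.9, 80.3 |
| 5.9% | 0.5 | 50.5, 49.1 | 26.4, 24.6 | 80.9, 78.2 |
| 5.9% | 1 | 50.1, 49.0 | 25.1, 24.6 | 82.3, 78.2 |
| 5.9% | 2 | 49.2, 48.9 | 23.5, 24.4 | 83.5, 78.2 |

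The 12-month estimate falls by 0.1 to 1.4 points, the 24-month estimate moves by -1.8 to +0.9, and the share with a counted event falls by 1.4 to 5.3 points. Even with equal later hazard, 12-month PFS falls slightly, because affected patients leave the risk set over an interval in which they are known to be event-free.

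**The case against.** **The row may mean only that this PD is not counted.** The sentence introducing Table 13 concerns patients alive and progression-free at cut-off, and a patient with a later PD or death is not one of them. No SAP text calls the censoring permanent. This stands to the extent that the loss of later events is inferred from the absence of a resumption rule. It does not clear the row. Table 13 also censors patients who have died or progressed after missed visits, so the introductory sentence does not limit the table. A row meaning only to disregard the PD would need no censoring outcome, date or reason. Two programmers could produce different INV curves.

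**Later data may not exist.** This stands in part. SAP 20.9 notes that PFS follow-up stops with treatment. For patients continuing MOR00208 despite recorded progression, Protocol 6.3 and 7.2.3 limit eCRF capture to antineoplastic therapy and AEs, and footnote 17 of the assessment schedule makes response scans not applicable. Later scans exist only for patients who stay on the normal schedule. For the others, what can be lost is a later death, which OS still captures.

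**The case is rare and the analysis supportive.** This largely stands. The first on-treatment PET in the schedule is C12D28, so the row needs an added, C12D28 or EOT PET. INV PFS appears both beside the IRC analysis and as a sensitivity analysis. No hypothesis is tested. With 80 patients, an approximate 95% half-width around 50% is 1.96 x sqrt(0.25/80) = 11 points, well above the shifts shown.

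**Stronger readings to avoid.** A reader might infer that the case is common, because Protocol 6.6.2.3 says "TFR is an expected toxicity with LEN, especially in patients with a high tumour burden and may mimic disease progression". The same section directs that flare be recorded as an adverse event and not as progression, so flare handled per protocol does not trigger the row. A reader might also extend the point to TTP, but SAP 10.5.2 has its own censoring text without this row. Lastly, a reader might expect the rule always to create IRC/INV discordance. Not counting an unconfirmed PD agrees with an IRC that found none; discordance arises only if a later event is dropped.

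**Conclusion.** The concern holds for INV PFS and the INV DoR sensitivity analysis. Followed literally, the row leaves the refuting PET uncredited, drops any later progression or death, and departs from the PFS definition in SAP 10.2.2. The main PFS analysis includes INV, and no planned analysis repairs the row, so it should be changed. It does not threaten the trial's main conclusions: the primary ORR, all IRC analyses and OS are untouched.

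The effect is probably small. The number of affected patients is not in the documents, and the shifts of roughly one to two points at most rest on the assumed 3% to 6% share and the other simulation inputs. The direction of bias depends on the affected patients' later hazard, which is unknown, so the documents do not support a claim that INV PFS is inflated or deflated.

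**What to change.** Replace the Table 13 row with a rule that:

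- a non-PET PD not confirmed by a following PET is not counted as PD and takes the PET response;
- the PET counts as an adequate assessment if its response is CR, PR or SD;
- the patient stays at risk until the next PD, death or another Table 13 censoring reason.

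Amend SAP 6.9 to match, so that an unconfirmed non-PET PD no longer fixes the progression date. Apply the rule to INV PFS and INV DoR, and keep the present rule as a sensitivity analysis.

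The cost is a small change to SAP wording and derivation logic, and no new data are needed. Where a patient left the normal assessment schedule, the rule restores only what was collected.

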13.1.1 Identification of two or more missing tumour assessments

If death or progression happens after two or more missed Tumour Assessments (TA), then the event is censored.

- An event occurring after two or more missing assessments or non-adequate tumour assessments will be censored on the date of last adequate tumour assessment.
- In one of the sensitivity analyses for PFS, an event occurring after two or more missing assessments is back-dated to the date of next scheduled assessment. The date of next scheduled assessment is the date of the last adequate tumour assessment plus the protocol specified time interval for assessments.
- If the patient has an EOT after two missed assessments without an event, then the patient will be censored for PFS at the last assessment and the censoring reason will be 'Adequate assessment no longer available'.
- Table 14 shows the maximum time [days] that can elapse between two response assessments without resulting in censoring.

Table 14: Time windows for missing response assessments

Missed tumor assessments	No tumor assessment between	Censored at
C3D1, C5D1	C1D1, C1D1 + 114 days (4 x 28 + 2)	C1D1
C5D1, C7D1	C3D1, C3D1 + 115 days (4 x	C3D1

STATISTICAL ANALYSIS PLAN

 MorphoSys AG
 MOR208C203

	28 + 1 + 2)	
C7D1, C10D1	C5D1, C5D1 + 144 days (5 x 28 + 2 + 2)	C5D1
C10D1, C12D28	C7D1, C7D1 + 173 days (6 x 28 + 2 + 4 - 1)	C7D1
C12D28, C15D1/C16D1	C10D1, C10D1 + 186 days (6 x 28 + 2 + 2 + 14)	C10D1
C15D1/C16D1, C18D1/C19D1	C12D28, C12D28 + 184 days (6 x 28 + 14 + 2)	C12D28
C18D1/C19D1, C21D1/C22D1	C15D1/C16D1 + 172 days (6 x 28 + 4)	C15D1/C16D1
C21D1/C22D1, C24D1/C25D1	C18D1/C19D1 + 172 days (6 x 28 + 4)	C18D1/C19D1
C24D1/C25D1	C21D1/C22D1 + 451 days (3 x 28 + 2 + 365)	C21D1/C22D1
Tumor assessments in Year 3 and Year 4 after treatment initiation*	C24D1/C25D1 + 730 days (2 x 365)	C24D1/C25D1

*Apply this interval also for assessments after C24D1/C25D1

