⁹After 30-Day Follow-up Visit, a call will be made to the patient (or the patient's family) every 90 days for at least 5 years from Cycle 1 Day 1 to inquire about the patient's status, second primary malignancy (SPM) and information on any antineoplastic therapies utilised since discontinuation of study treatment.

¹⁰After disease progression has been recorded, only anticancer treatments and, in case of an AE, other relevant concomitant medications (at the discretion of the investigator) should be entered. Before and up to the End of Treatment Visit, the complete concomitant medication needs to be recorded.

¹¹A limited PE (L) will be performed on Day 1 of each Cycle, every 12 weeks \pm 2 days from the previous PE.

¹²Anti-MOR00208 antibody sample and MOR00208 PK sample (pre-dose only) will be taken in odd numbered additional treatment cycles only (i.e. treatment Cycles 13, 15, 17, 19, 21, 23). No samples to be collected after Cycle 23.

¹³Disease assessment by CT/MRI of neck, chest, abdomen & pelvis with iv contrast during additional treatment phase; Cycles 13-24: approximately every 3 months \pm 2 days from the previous scan. First assessment during this phase can be done directly 3 months after Cycle 12 D28 PET/CT assessment. Thus, this assessment is not needed at Cycle 13 Day 1, and an interval longer than \sim 3 months is acceptable for Cycle 16 Day 1 assessment; Cycle 25 onwards: approximately once every year \pm 2 weeks from the previous scan. Images will have to be transferred to the central imaging laboratory.

¹⁴In case the patient is withdrawn from treatment before the end of Cycle 12 for reasons other than progression of disease. PET/CT is only required at the EOT visit if it was not performed in the cycle before the end of treatment visit.

¹⁵Bone marrow assessment during additional treatment phase (Cycles 13 to 24) approximately every 3 months \pm 2 weeks from the previous assessment; to be performed to confirm a CR only in those patients who had known bone marrow involvement prior to dosing. Refer to [Section 7.2.14.2](#) for further details.

¹⁶HBV-DNA to be measured and re-measured only if anti-HBc was positive at screening. If HBV-DNA is positive at screening, or during treatment, please see [Section 7.2.13.2](#).

¹⁷Not applicable for patients who continue receiving MOR208 despite disease progression.

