6.14 Efficacy Assessments

6.14.1 Response criteria

The efficacy variables / endpoints will be evaluated through central review by an Independent Radiology/Clinical Review Committee (IRC) that will apply the revised response assessment criteria based on the guidelines of the IWG reported by Cheson et al. (2007) (see **Error! Reference source not found.**). The review process will be defined in the IRC Charter.

Local assessment of efficacy response (Cheson criteria) will be required in addition to central review at the beginning of Cycle 3, Cycle 5, Cycle 7, and Cycle 10, at the end of Cycle 12 (for decisions concerning the additional Cycle 13 through Cycle 24 MOR00208 treatment) and at the EOT Visit (to determine whether the disease has progressed). During the treatment phase from Cycle 13 onwards (MOR00208 monotherapy phase) tumour response assessments will be performed as follows: for Cycles 13 - 24 local assessments of response will be done approximately every 3 months \pm 2 days from the previous scan. First assessment during this phase can be done directly 3 months after Cycle 12 Day 28 PET/CT assessment. Thus, the first response assessment after Cycle 12 is not needed at Cycle 13 Day 1. Moreover, the first assessment during the MOR00208 monotherapy phase can generally happen later than 3 months after the Cycle 12 Day 28 assessment. From Cycle 25 onwards local assessments of response will be performed approximately once per year \pm 2 weeks from the previous scan. Efficacy will be evaluated in terms of (best) ORR (primary endpoint), DCR, DoR, PFS, OS, TTP and TTNT (secondary endpoints) based on both INV and IRC response assessment. For definitions, see Sections 9 (primary endpoint) and 10 (secondary endpoints).

Table 3: Definition of Response Criteria (Cheson et al., 2007)

Response	Definition	Nodal masses	Spleen, liver	Bone marrow
CR	Disappearance of all evidence of disease	a) FDG-avid or PET positive prior to therapy; mass of any size permitted if PET negative b) Variable FDG-avid or PET negative; regression to normal size on CT	Not palpable, nodules disappeared	Infiltrate cleared on repeat biopsy; if indeterminate by morphology, immunohistochemistry should be negative

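### SAP Table 14's 451- and 730-day limits omit the 2-week window for yearly scans, so an event after one missed scan can be censored as if two were missed

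*SAP*

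**What the plan says.** The governing rule in SAP 10.2.4 (subsection 13.1.1) is a count: "If death or progression happens after two or more missed Tumour Assessments (TA), then the event is censored". The SAP applies it through elapsed days: "Table 14 shows the maximum time [days] that can elapse between two response assessments without resulting in censoring". SAP Table 13 dates the censoring to the last adequate tumour assessment. DoR uses the same table (SAP 10.3.3).

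The rows after Cycle 12 are:
- from C12D28: "C12D28, C12D28 + 184 days (6 x 28 + 14 + 2");
- from C15/C16, with the same figure from C18/C19: "C15D1/C16D1 + 172 days (6 x 28 + 4");
- from C21/C22: 451 days, built as 3 x 28 + 2 + 365;
- from C24/C25 and all later scans: "C24D1/C25D1 + 730 days (2 x 365").

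On the schedule, SAP 6.14.1 says that in Cycles 13 to 24 "local assessments of response will be done approximately every 3 months", with a 2-day window counted from the previous scan. Protocol Table 5, footnote 13, has for the later phase "Cycle 25 onwards: approximately once every year", with 2 weeks either side. SAP 6.14.1 repeats the 2 weeks, and the footnote to SAP Table 12 says that this window "is allowed by the protocol for these assessments".

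**The concern.** Each limit in Table 14 sits at or near the latest date of the second scheduled scan after the last adequate one. A patient who misses one scan and attends the next on time should therefore fall inside the limit. Only a patient who misses both should fall outside it. That works only if the limit includes the visit windows, and up to Cycle 12 it does. For example, the C5D1 row adds 2 + 2 days and the C7D1 row adds 2 + 4.

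The two rows that involve a yearly scan break this pattern. The 730-day row adds no window. The 451-day row adds the 2 days of the three-monthly scan but not the 14 days of the yearly one.

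At stake is a loss of events in one direction. A progression seen on an in-window scan, or a death before that window closes, becomes a censoring dated back to the previous adequate scan, more than 14 months (451 row) or about two years (730 row) earlier. The 48-month PFS and DoR rates in Addendum 8 rest on this follow-up.

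**Working it through.** **Inputs.** The Table 14 sums. Yearly scan: 365 days, window 14 days (Protocol Table 5 footnote 13; SAP 6.14.1; SAP Table 12 footnote). Three-monthly scan: window 2 days (SAP 6.14.1). Three months: either 3 x 28 = 84 days (the cycle labels in Table 14) or 3 x 30.4375 = 91.3 days (month length in SAP 6.6). Delay before Cycle 13: up to 14 days, plus or minus 2 (Protocol Table 5).

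**Step 1: reproduce the plan's figures.** All ten bracketed sums are correct as sums: 114, 115, 144, 173, 186, 184, 172, 172, 451 and 730. The question is what the sums leave out.

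**Step 2: in-window range of the second scan after the last adequate one.** This is two scheduled intervals, minus or plus both windows.

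| Row | Three months as | Earliest | Nominal | Latest | Latest minus limit |
|---|---|---|---|---|---|
| 730 | not used | 2 x (365 - 14) = 702 | 730 | 2 x (365 + 14) = 758 | 28 |
| 451 | 84 | 84 - 2 + 365 - 14 = 433 | 449 | 84 + 2 + 365 + 14 = 465 | 14 |
| 451 | 91.3 | 440.3 | 456.3 | 472.3 | 21.3 |
| 172 | 84 | 2 x (84 - 2) = 164 | 168 | 2 x (84 + 2) = 172 | 0 |
| 172 | 91.3 | 178.6 | 182.6 | 2 x (91.3 + 2) = 186.6 | 14.6 |
| 184 | 84, with the Cycle 13 delay | not needed | 14 + 168 = 182 | 14 + 2 + 168 + 2 = 186 | 2 |
| 184 | 91.3 | 178.6 | 182.6 | 186.6 | 2.6 |

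If only the attended scan's window is counted, the 730 row's latest date is 730 + 14 = 744, still 14 days over.

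**Step 3: share of in-window second scans past the limit.** Assume that dates are uniform and independent within their windows; the documents do not say so.
- 730 row: about 50%.
- 451 row: about 43% with 84 days (0.5 - 2/28), about 69% with 91.3 days.
- 172 rows: none with 84 days, all with 91.3 days.
- 184 row: about 12% and 21%.

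**Step 4: where on the curve this falls.** C21D1 is 20 x 28 = 560 days after C1D1, and C24D1 is 23 x 28 = 644.
- The earliest PFS events lost are at about 560 + 451 = 1011 days (33.2 months) and 644 + 730 = 1374 days (45.1 months).
- The censoring moves such a patient back to 560 days (18.4 months) or 644 days (21.2 months).
- The DoR clock starts at response. For a response first seen at C10D1 (9 x 28 = 252 days), day 1011 is 759 days into response, or 24.9 months.

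**The case against.** The strongest reply has four parts.

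**The count governs, and the tail is late.** The text already speaks of two missed assessments, and the main PFS time points stop at 30 months (SAP 10.2.5), before either row can remove a PFS event. The timing stands: at those points the only effect is earlier censoring. It does not cover the 48-month rates, nor the 30-month DoR rate for later responders (step 4). The count does not settle the matter either, because Table 14 is presented as the operative limit and contradicts the count in these two rows.

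**Sensitivity analyses exist.** SAP 10.2.6 restores deaths after more than one missed visit as PFS events. SAP 20.9 counts death or progression after two or more missed visits as events for PFS and DoR. Censoring reasons are tabulated for PFS (SAP 10.2.5) and listed for DoR (SAP 20.7.4), so the affected patients can be found. All of this helps. But 10.2.6 restores only deaths and only for PFS, while 20.9 changes three rules together and back-dates the event. The main analysis keeps the error.

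**Not every case is caught.** Correct. In the 730 row a second scan on or before its nominal date passes. The same holds in the 451 row if three months is 84 days.

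**The other post-Cycle-12 rows may be right.** A reader might infer that every limit after Cycle 12 is too short. The documents do not support that. On the table's own cycle labels, 172 is exactly two 84-day intervals with both 2-day windows. It is short only if three months means calendar months. SAP 6.6 gives its month length for reporting durations, though Protocol Table 5 equates three-monthly survival calls with 90 days in footnote 9. That is an ambiguity, not an arithmetic error. The 184-day row contains the nominal dates and is short by 2 to 2.6 days at the window edge. A reader might also compute 169 + 14 + 4 + 2 = 189 for it, but that counts the step to Cycle 13 twice and adds a window for C12D28 although the count starts on that scan's own date.

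**Conclusion.** The point holds for the 451- and 730-day rows. Both leave out a window that the protocol and the SAP state, and the shortfall is 14 days (84-day reading) and 28 days. A progression or death after a single missed scan can then be censored as if two had been missed. The shares of about 43% and 50% apply only to patients who have missed one scan and attend the next in its window, and they rest on the uniform-timing assumption.

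The number of events affected cannot be derived. The plan gives no missed-scan rate, and any count would need that rate, the number of patients still followed, and their progression rate. The direction is known: events become censorings, which lifts the late part of the PFS and DoR curves.

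For the 172- and 184-day rows the finding is only that the length of three months must be stated.

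**What to change.** 1. In Table 14, change 730 to 758 (2 x (365 + 14)) and 451 to 465 (84 + 2 + 365 + 14). In the 451-day row, also name the first yearly scan as the second missed assessment: the row now lists only C24D1/C25D1, while its sum spans two scans.
2. State whether scanning every three months means 84 days (three cycles) or about 91 days.
   - With 84 days, the 172-day rows stay and the C12D28 row becomes 186.
   - With 91.3 days, the 172- and 184-day rows become about 187 and the 451-day row about 472.
3. Say how the first scan after Cycle 12 is handled. Protocol 7.2.14 and SAP 6.14.1 let it fall later than three months with no upper bound, which no fixed limit can fully cover.

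The cost is two numbers and a sentence or two, with a small change to the PFS and DoR derivations. A few late censorings may become events, so PFS and DoR may be slightly shorter. A listing of patients whose gap lies between the present and the corrected limits would show the effect directly.
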